- 2. We use the UW-ICTR for local data monitoring oversight. This plan includes the use of the ICTR OnCore clinical research management (OnCore-CRM) system which allows more efficient tracking of protocols and protocol subjects. ICTR OnCore-CRM is a secure, web-based, customizable information system that addresses issues related to the costs and complexities associated with conducting clinical trials. It provides fully integrated clinical data management, study administration, and financial management capabilities for a portfolio of clinical trials. The ICTR OnCore-CRM system is specifically designed to improve the efficiency and effectiveness of clinical research at large research centers by facilitating core activities such as study setup and activation, accrual, clinical data collection and analysis, data and safety monitoring, financial management, and regulatory compliance.

Adverse Event Reporting:

Adverse Events

An adverse event is any untoward medical occurrence in a patient or clinical investigation subject, temporally associated with the use of a medicinal product, whether or not considered related to the study procedure or medicinal product. An AE can therefore be any clinically significant and unintended sign (including an abnormal laboratory finding), symptom, or disease (new or exacerbated) temporally associated with the study product or procedure. Unexpected side effects that are not clinically significant (NCS) will not be considered adverse events. Anticipated day-to-day fluctuations of the conditions or diseases will not be considered an adverse event, unless they:

- 1. fulfill the definition of a serious adverse event, or
- 2. unexpectedly worsen, requiring medical intervention other than the use of the rescue medication, or
- 3. result in discontinuation of subject from the study.

The Investigator and study staff will record adverse events representing (1) unexpected, clinically significant reactions or (2) abnormal worsening of expected symptoms on an adverse event form to be maintained in the subject's research chart, regardless of the relationship to investigational product or procedures. The form will include observation date and resolution date.

The common, uncommon, rare, and very rare side effects indicated in the Safety section of the protocol will be recorded as adverse events if deemed clinically significant by a study physician. If a study physician determines that a clinically significant side effect renders study activities unsafe, subjects may be temporarily or permanently excluded from study participation.

All adverse events will be graded by severity using the National Cancer Institute (NCI) Common Terminology Criteria for Adverse Events (CTCAE), Version 4.0, May 28, 2009 listed below:

Grade 1= Mild adverse event Grade 2= Moderate adverse event Grade 3= Severe and undesirable adverse event Grade 4= Life threatening or disabling adverse event Grade 5= Death

Assessment of Causality

The principal or co-investigator will assess the relationship between the study and the occurrence of each AE/SAE. The investigator will use clinical judgment to determine the relationship. Alternative causes, such as natural history of the underlying diseases, concomitant therapy, other risk factors and the temporal relationship of the event to the study will be considered and investigated.

The relationship between as adverse event and the study will be recorded on the study adverse event form. The NCI-CTCAE provides the following descriptors and definitions for assigning relationship. This NCI nomenclature will be used but causality will be judged by the investigators in the context of asthma.

Code	Descriptor	Definition
1	Unrelated	The event is clearly not related to the study
2	Unlikely	The adverse event is doubtfully related to the study
3	Possible	The adverse event may be related to the study
4	Probable	The adverse event is likely related to the study
5	Definite	The adverse event is clearly related to the study

Disease- or Study-Related Events or Outcomes

Definition of a Serious Adverse Event

A serious adverse event (SAE) or reaction is defined (21 CFR 312.32 (a)) as any adverse event occurring at any dose that suggests a significant hazard, contraindication, side effect or precaution. This includes, but may not be limited to any of the following events:

- Death: A death occurring during the study or which comes to the attention of the Investigator during the protocol-defined follow-up after the completion of therapy, whether or not considered treatment-related, must be reported.
- Life-threatening: Any adverse therapy experience that places the participant or participant, in the view of the Investigator, at immediate risk of death from the reaction as it occurred.
- Hospitalization or prolongation of existing hospitalization.
- Persistent or significant disability/incapacity.
- Congenital anomaly/birth defect.
- An event that required intervention to prevent permanent impairment or damage.

An important medical event that does not meet the criteria listed above may be considered an SAE when, based upon appropriate medical judgment, it may jeopardize the participant and may require medical or surgical intervention to prevent one of the outcomes listed above.

Medical and scientific judgment should be exercised in deciding whether reporting is appropriate in other situations. These situations might include an important medical event that may not be immediately life-threatening or result in death or hospitalization, but may jeopardize the subject or may require medical or surgical intervention to prevent one of the other outcomes listed in the above definition.

Study Related Non-serious and Unexpected or Expected Adverse Event Reporting

All non-serious and unexpected adverse events will be kept in an adverse event log and reported annually. Other adverse events that are both not serious and expected will not be reported. These are the expected adverse events listed in the protocol and consent as possible results from a study procedure. The investigator will meet all local reporting requirements as dictated by the UW IRB.

Individual stopping rules have been outlined that address the intensity or persistence of these adverse events.

Individual and Overall Study Stopping Rules:

Based upon the definition of Serious Adverse Event as described in 21 CFR 312.32.

Individual Safety Stopping Rules

Individuals will be stopped from the study if the following events occur:

- The subject requests that a particular procedure be stopped or expresses a desire to withdraw from the study.
- Failure to recover to within 80% of baseline FEV₁ at discharge from any study visit. Albuterol therapy may be employed to assist in recovery.
- Any serious and unexpected adverse event or any event that, in the opinion of the investigator, poses undue risk to the subject.

Overall Safety Stopping Rules

The study will be stopped if:

- 1. A research related death occurs in any subject.
- 2. An event occurs that the investigator feels warrants halting of the study.
- 3. The same or similar serious and unexpected adverse event associated with the study that occurs in at least two subjects. This may include a potentially life-threatening event, event requiring hospitalization, or any event that may potentially result in serious harm to other research subjects.
- 4. For non-serious adverse events, if more than 20% of research volunteers meet the individual safety stopping rules listed above, and are withdrawn from the study, the protocol will be halted. The NIH (and IRB if required) will be notified and appropriate modifications to the protocol will be made.

Ethical Considerations:

- This study will be conducted in compliance with current Good Clinical Practice of the International Conference on Harmonization and the ethical principles of the Declaration of Helsinki. The study will begin only after the UW Health Sciences Institutional Review Board (IRB) has granted approval.
- 2. The UW IRB approved consent form will state that subjects may withdraw from this study at any time without any change in the quality of their medical care or loss of benefits.
- 3. Each subject is required to sign a HIPAA Research Authorization at the time of consent. This authorization clearly outlines who will have access to specified protected health information. The information obtained in these studies is not particularly sensitive. However, data will coded by subject identification numbers and any key linking this code number to subject identifiers will have access limited to the investigator and key study personnel all of whom have had HIPAA training required by the University of Wisconsin. Data will be stored in files and a computer database, both in a locked location with access only by study personnel. Data obtained from the study may be published in scientific journals or presented in scientific meetings but results will be coded so individuals are not identified. Records will be retained by the Principal Investigator for at least two years after the investigation is discontinued and the FDA is notified. This is in accordance with US FDA Regulation (21CFR 312.62 (c)).

Calendar of Events:

	Visit(s)		
Procedure	V1	V1a	V2

	Day 1 ^(x)	Day 1 ^(y)	Day 2 ^(y)
Informed Consent Process	Х		
MRI Simulation	Х		
Medical History		X ^{AN}	X ^{AN}
Review of Concomitant Medications		X ^{AN}	X ^{AN}
Physical Exam		X ^{AN}	X ^{AN}
Pregnancy Test		X ^{AN}	X ^{AN}
Vital Sign Measurement		X ^{AN}	X ^{AN}
eNO		X ^{AN}	X ^{AN}
Spirometry		X ^{AN}	X ^{AN}
Blood Draw ^A		X ^{AN}	X ^{AN}
Eligibility Review		X ^{AN}	X ^{AN}
Questionnaires ^B		X ^{AN}	X ^{AN}
Cognitive Function Tests		X ^{AN}	X ^{AN}
fMRI Scan		X ^{AN}	X ^{AN}
Adverse Event Symptom review		X ^{AN}	X ^{AN}

Calendar Foot Notes	
(x)	V1 - Consent, MRI Screen, MRI Simulation
(y)	All procedures marked "As Needed" must occur once, all on the same visit. All AN procedures will take place at either V1a or V2. (N/A for subjects deemed ineligible at V1)
Α	Measurement of gene expression (PBMC) via RNA sequencing; RNA analysis of plasma
В	Asthma and Psychological Questionnaires: BDI, BAI, STAI, PSWQ, PANAS, PSS, ACQ
AN.	As Needed

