Urine Collection. If the subject is a female of child-bearing potential, a urine pregnancy test will be conducted to exclude pregnancy prior to performance of certain study procedures.

Exhaled nitric oxide (eNO): Exhaled NO has recently been shown to be a useful marker of airway inflammation in asthma, in particular because its rise frequently precedes that of lung function decline and thus is valuable in preventative care (Hoffmeyer et al., 2009). Fraction of exhaled NO (parts per billion) will be measured in breath condensate, following American Thoracic Society guidelines (Silkoff et al., 1997; Anonymous, 1999), at a flow rate of 50 mL/s, with a rapid-response chemiluminescent analyzer (NIOX System; Aerocrine, Solna, Sweden; Silkoff et al., 2004).

Spirometry (FEV₁, FVC, FEV₁/FVC, and FEF_{25-75%}): Spirometry will be conducted according to ATS guidelines. The variables FEV1, FVC, FEV1/FVC and FEF25-75 will all be recorded from the "best" effort, defined as the effort with the highest sum of FEV1 + FVC. FEV1 will be used as the global indicator for spirometry, and this variable will be partitioned into FVC and FEV1/FVC components.

Blood sample (up to 30 ml):

a. CBC with differential: this will include a cell differential count of eosinophils, neutrophils, macrophages, and lymphocytes.

b. Measure of gene expression in peripheral inflammatory cells by RNA seq: Peripheral blood mononuclear cells (PBMC) from severe asthmatic subjects will be prepared on Ficoll density gradient from 20 ml of Lithium heparinized whole blood. 10 to 20 million PBMC will be

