recovered and cultured in RPMI with 10 % FBS in 24-well plates for 4 h or 24 h. To evaluate peripheral blood T lymphocyte activatability, PBMC will be cultured with (for 4 h) or without (for 24 h) anti-CD3 plus anti-CD28 (each at 1 µg/ml). Peripheral blood monocyte activatability will be evaluated by LPS (1 µg/ml) stimulation for 4 h. In addition, sensitivity to corticosteroids will be analyzed by adding 10-9, 10-8 and 10-7 M of dexamethasone to PBMC 15 minutes before activation with anti-CD3 plus anti-CD28 and LPS. Cells will be harvested in buffer RLT (Qiagen) and stored at -80°C until they undergo total RNA extraction. Total RNA guality control and RNAseq will be performed by the Biotech Center at UW-Madison on total RNA from unactivated PBMC, and LPS- and anti-CD3/CD28-activated cells, using Illumina HiSeg 2500. SegMAn NGen13 and Array Star13 softwares will be used to analyze gene expression. Analysis: Principal component analysis (PCA) will be performed to group the genes which expressions change concomitantly among the asthmatic subjects. The groups of genes will then be associated with markers of the neurocircuitry activity (MRI, questionnaires). The genes part of PCA and associated with the neurocircuitry activity will be further analyzed using the Ingenuity Pathway Analysis (IPA) system from Qiagen. PBMC treated with dexamethasone will be analyzed by RT-PCR, to measure expression levels of pro-inflammatory (IL-1, TNF, IL-6, IL-8), Th-2 (IL-13), Th-17 (IL17A) and Th-1 (IFN-y) cytokines. Expression levels will then be analyzed for associations with the neurocircuitry activity.

c. plasma for RNA analysis

Asthma and psychological questionnaires: Participants will complete self-report questionnaires that assess life stressors, perceived stress, emotional style, and symptoms of anxiety and depression. These questionnaires may include the following: Beck Depression Inventory, Beck Anxiety Inventory, State-Trait Anxiety Inventory, Penn State Worry Questionnaire, Positive and Negative Affect scale, Perceived Stress Scale, and the Asthma Control Questionnaire.

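### Bulk PBMC expression is to be linked to brain measures with no term for cell mix, so an association, mainly for the LPS readout, could reflect monocyte share; reporting it unadjusted and adjusted is a cheap improvement

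*Combined protocol and SAP*

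**What the plan says.** All of this stands in the combined protocol and SAP, under Procedures, Blood sample.

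- **Item a, blood count.** "this will include a cell differential count of eosinophils, neutrophils, macrophages, and lymphocytes". Monocytes are not named.
- **Item b, material.** Mononuclear cells are taken from a Ficoll gradient and cultured. No step separates or counts the cell types in that fraction.
- **Item b, labels.** Each readout from the mixture is assigned to one cell type. For T cells: "To evaluate peripheral blood T lymphocyte activatability, PBMC will be cultured with (for 4 h) or without (for 24 h) anti-CD3 plus anti-CD28". For monocytes: "Peripheral blood monocyte activatability will be evaluated by LPS".
- **Item b, sequencing.** RNA-seq is done "on total RNA from unactivated PBMC, and LPS- and anti-CD3/CD28-activated cells".
- **Item b, analysis.** "Principal component analysis (PCA) will be performed to group the genes which expressions change concomitantly among the asthmatic subjects". Then: "The groups of genes will then be associated with markers of the neurocircuitry activity (MRI, questionnaires", closing the bracket. For the cytokines measured by RT-PCR in the dexamethasone-treated wells: "Expression levels will then be analyzed for associations with the neurocircuitry activity".

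Neither association is given a covariate.

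**The concern.** In a mixture of cells, the signal of a transcript made by one cell type is the share of that cell times the amount made per cell. Genes of one cell type therefore rise and fall together across subjects when the share of that cell varies. A principal component analysis across subjects is built to find such joint variation, so a component can describe cell mix. RT-PCR cytokine levels are open to the same effect.

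Whether this matters for the brain question depends on a second condition: the mix must also be related to the neurocircuitry marker. A route can be imagined. Severe asthma is defined by high-dose inhaled or systemic corticosteroid treatment, and the hypothesis is that neurocircuitry intensity rises with severity. If steroid exposure also shifts blood cell mix, severity could drive both. That last step is an assumption, not something the documents report.

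At stake is the meaning of a positive finding. An association described as monocyte activatability, and the pathway analysis built on it, could describe how many monocytes a subject has and not how those cells respond.

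**Working it through.** The plan states no figure on this point, so there is none to reproduce. The check has a reading part and an illustrative part.

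**1. Reading.** The whole document was read for cell sorting, a PBMC subset count, deconvolution, marker-gene scores, a cell-fraction covariate, or a stated activated-minus-unactivated contrast within subject. None is there. Data Storage refers in general terms to blood cell numbers and types, without naming the types or tying them to the expression analysis.

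**2. Effect of mix on one transcript.** Assume that monocytes make up 10% of PBMC in one subject and 20% or 30% in another, with lymphocytes as the rest and the same response per cell.

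- Monocyte-only transcript: 0.20/0.10 = 2 (log2 = 1.0); 0.30/0.10 = 3 (log2 = 1.58).
- Lymphocyte-only transcript: 0.80/0.90 = 0.89 (down 11%); 0.70/0.90 = 0.78 (down 22%).

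The LPS readout is thus far more exposed than the anti-CD3/CD28 readout.

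**3. Correlation with the brain measure produced by mix alone.** Let log bulk expression = log monocyte share + per-cell response, with the per-cell response unrelated to the brain measure. Let ρ be the correlation of log share with the brain measure, and k the SD of log share divided by the SD of per-cell response. Then

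induced r = ρ × k / √(1 + k²).

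Example: ρ = 0.5, k = 2 gives 0.5 × 2/√5 = 0.45.

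**4. False-positive rate.** Pearson test, two-sided 0.05 (assumed; the plan gives no alpha or sidedness), 20,000 simulations, with n = 22 (assumed completers) and n = 30 (target), both from the sample size section. The values of ρ and k are assumptions.

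| ρ | k | induced r | n = 22 | n = 30 |
|---|---|---|---|---|
| 0 | 0.5 to 2 | 0 | 0.048 to 0.051 | 0.048 to 0.054 |
| 0.3 | 0.5 | 0.134 | 0.088 | 0.110 |
| 0.3 | 1 | 0.212 | 0.156 | 0.200 |
| 0.3 | 2 | 0.268 | 0.225 | 0.307 |
| 0.5 | 0.5 | 0.224 | 0.170 | 0.227 |
| 0.5 | 1 | 0.354 | 0.372 | 0.500 |
| 0.5 | 2 | 0.447 | 0.574 | 0.722 |

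**5. What adjustment achieves.** With the share as covariate, measured without error, the rate is 0.047 to 0.053 in every row. If the covariate has reliability R, the partial correlation that remains is

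ρg(1 − R) / √[(1 − ρ²R)(1 − g²R)], with g = k/√(1 + k²).

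For n = 30 and k = 2 (g = 0.894):

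| ρ | R | remaining r | error, adjusted | error, unadjusted |
|---|---|---|---|---|
| 0.5 | 0.7 | 0.22 | 0.21 | 0.72 |
| 0.5 | 0.5 | 0.31 | 0.38 | 0.72 |
| 0.3 | 0.7 | 0.13 | 0.10 | 0.31 |
| 0.3 | 0.5 | 0.18 | 0.15 | 0.31 |

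Adjustment helps in each case but does not restore 0.05 when the covariate is imperfect.

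**The case against.** Several points on the other side have weight.

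- **The count may well exist.** A reader might infer that monocytes will not be measured. The text does not support that: the list is introduced as what the count will include, which is not exhaustive, and macrophages stand where the blood phagocyte would be expected. This is probably a wording slip, and clerical by itself. Correcting it does not supply the missing analysis term.
- **Unactivated cells are sequenced too.** If activatability means change from the subject's own unactivated sample, part of the mix effect cancels for genes that the same cells express in both conditions. A comparison across dexamethasone concentrations within subject would cancel much of it as well. This is fair, but neither contrast is stated. The T-cell item sets 4 h with stimulus against 24 h without, and the RT-PCR text speaks of expression levels.
- **No bias is demonstrated.** A reader might infer that the brain associations will be biased. The documents give no data on how cell mix relates to neural activity, and at zero correlation the error rate stays at 0.05. The inflated rates above follow from assumed inputs. This stands in full.
- **The T-cell readout is not equally affected.** This stands too: about 11% down against a doubling when the monocyte share goes from 10% to 20%.
- **Adjustment is no proof.** The CBC fraction only approximates the mix after Ficoll separation. A shift in circulating cells may also be part of the inflammation under study, and losing significance with 22 to 30 subjects refutes nothing. Surviving adjustment should therefore not be the test for the word activatability.

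**Conclusion.** The concern holds in a limited form. The plan assigns bulk readouts to single cell types and takes gene groups and cytokine levels straight to association with neurocircuitry markers, with nothing for cell mix. Followed as written, it can present a difference in monocyte share as a difference in response per cell, mainly for LPS.

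The size is conditional. It rests on the monocyte share varying between subjects, on that share being related to the brain measure, and on the assumed k. At ρ of 0.3 to 0.5 the induced correlation can reach 0.45, close to the association of .5 that the sample size section calls moderate, if that figure is read as a correlation. At ρ = 0 the cost is noise only.

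The documents do not support the stronger conclusions that monocytes go uncounted, that both readouts are equally compromised, or that the associations are in fact biased. This is an exploratory analysis within a pilot whose stated purpose is the comparison across asthma severities. The point is a cheap improvement, not a defect that undermines the study.

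**What to change.** 1. In item a of Blood sample, name monocytes in the differential, or confirm that this is what macrophages was meant to say.
2. In item b, state that each association of a PCA gene group or RT-PCR level with an MRI or questionnaire marker is reported twice: unadjusted, and adjusted for monocytes/(monocytes + lymphocytes) from the CBC of the same draw.
3. Describe a result that changes materially on adjustment as possibly due to cell mix. Do not make survival of adjustment a condition for using the word activatability.

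**Cost.** No new test, if the CBC reports monocytes as expected. One degree of freedom is used: residual degrees of freedom go from 20 to 19 with 22 subjects and from 28 to 27 with 30. The correction is partial, because the CBC fraction only approximates the post-Ficoll mix, and it does not correct for the T-cell share of lymphocytes. The report should state both limits.

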Breach of confidentiality: There is a risk of breach of confidentiality. In order to protect against this risk, all data will be stored on a secure, password protected network. All data will be identified using unique identification numbers, not names, date of birth, or other identifiable information. In files where identifiable information is linked to the unique ID number, only staff members who specifically use this information for contacting participants, etc. will have access.

Email address: We are requesting the subject's email address so we can communicate study visit reminders or changes with them. Email is generally not a secure way to communicate about a subject's health as there are many ways for unauthorized users to access email. The subject is instructed to avoid sending sensitive, detailed personal information by email. Email should also not be used to convey information of an urgent nature. If the subject needs to talk to someone immediately, they are instructed to contact a pulmonary research study coordinator at [contact]. Or can also contact the Principal Investigator of the study [name] at [contact]. The subject does not have to provide their email address to participate in this study. The subject can also request at any time that email no longer be used to communicate about the study, without any loss or penalty.

Sample Size Calculation and Data Analysis:

This is a pilot study. Our target sample size is total 30 individuals with severe asthma. The attrition rates in our prior research have been low (0-7%) and our power calculations assume that at least 22 subjects (12% attrition) complete the study. For continuous outcomes in general, including airway cellular and molecular inflammatory responses to stimulation, and measures of neural activity (e.g. % signal change in insula by fMRI), effect sizes for the relationship between neural activity and increases in inflammatory markers is expected to be large. In previous studies, we report associations between increases in activity in insula and ACC and peripheral measures of inflammation with effect sizes that range from .56 to .99. It should be noted that the extremely large effect sizes are, in part, a function of the small sample size and thus, the

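### T-cell activatability pairs 4 h stimulated PBMC with 24 h unstimulated PBMC, so any stimulated-versus-unstimulated measure is confounded with 20 h of extra culture

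*Combined protocol and SAP*

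**What the plan says.** The text is in the combined protocol and SAP, Procedures, Blood sample, item b (gene expression by RNA seq).

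- **General culture times.** Recovered cells are cultured "in 24-well plates for 4 h or 24 h".
- **T-cell pair.** The purpose is given as "To evaluate peripheral blood T lymphocyte activatability", and the same sentence says that "PBMC will be cultured with (for 4 h) or without (for 24 h) anti-CD3 plus anti-CD28".
- **LPS.** "Peripheral blood monocyte activatability will be evaluated by LPS", with a stimulation time of 4 h. No unstimulated control is named for it.
- **Dexamethasone.** Three concentrations are added shortly before activation, and these wells are read by RT-PCR. No separate culture time is given.
- **RNAseq.** Sequencing is run "on total RNA from unactivated PBMC, and LPS- and anti-CD3/CD28-activated cells". This sentence gives no culture time for the unactivated cells.
- **Analysis.** PCA is used to "group the genes which expressions change concomitantly among the asthmatic subjects"; the gene groups are then associated with MRI and questionnaire markers. No stimulated-minus-unstimulated contrast is written out.

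**The concern.** Activatability is a comparative idea: how far cells move from their resting state when stimulated. The with/without pairing, and the sequencing of an unactivated sample next to the activated ones, both point to such a comparison. But the resting sample has spent 20 h longer in culture. A gene whose expression drifts over those hours would look induced or suppressed even if anti-CD3/CD28 did nothing to it, and a real response could be hidden.

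At stake is the interpretation of an induced-gene list and of any per-subject activation score taken forward to the neurocircuitry markers. If no unstimulated well of matching duration is harvested for a subject, no later analysis can recover the separation for that subject.

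**Working it through.** **Inputs** (all from Blood sample, item b): anti-CD3/CD28 for 4 h; no anti-CD3/CD28 for 24 h; LPS for 4 h. Time gap: 24 − 4 = 20 h. The plan gives no figure of its own to reproduce for this assay.

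**Can the effects be separated?** For one gene, take an additive model. Let μ be expression in unstimulated cells at 4 h, δ the anti-CD3/CD28 effect, λ the LPS effect, and τ the effect of 24 h rather than 4 h in culture. The written conditions have these means:

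- anti-CD3/CD28, 4 h: μ + δ
- none, 24 h: μ + τ
- LPS, 4 h: μ + λ

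That is three means for four parameters (design matrix of rank 3 of 4). Neither δ nor λ can be estimated apart from τ. The possible readings compare as follows:

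| Reading | anti-CD3/CD28 − unstimulated | LPS − unstimulated | Unmatched contrasts |
|---|---|---|---|
| As written, 24 h culture is baseline for both | δ − τ | λ − τ | 2 of 2 |
| As written, but LPS is compared with its own 4 h control | δ − τ | λ | 1 of 2 |
| Two times transposed (stimulated 24 h, unstimulated 4 h) | δ + τ | λ | 1 of 2 |
| Unstimulated 4 h well added and used as baseline for both | δ | λ | 0 of 2 |

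Transposition leaves the rank at 3 of 4: LPS becomes matched, but anti-CD3/CD28 does not. Adding an unstimulated 4 h well to the written conditions gives rank 4 of 4, and both effects are then estimable.

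**What happens to correlations between subjects?** Write S4, U4 and U24 for one subject's stimulated 4 h, unstimulated 4 h and unstimulated 24 h expression. A score against the 24 h well is

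S4 − U24 = (S4 − U4) − (U24 − U4) = A − T.

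If T is the same in every subject, it drops out of any correlation with neural activity. If T varies, let v = var(T)/var(A) and c = corr(A, T), and assume that T is uncorrelated with neural activity. A true correlation r then becomes r / √(1 + v − 2c√v). Take r = 0.5, the magnitude in the power statement (Sample Size Calculation and Data Analysis):

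- If S4, U4 and U24 are independent with equal variances, then v = 2/2 = 1 and c = 1/2, because A and T share U4. Result: 0.5 / √(1 + 1 − 1) = 0.50, no change.
- If v = 0.25 and c = 0.5: 0.5 / √(1 + 0.25 − 0.5) = 0.5 / √0.75 = 0.58, an increase.

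Other values of v and c give a decrease. The documents supply neither quantity; both are assumptions here, used only to show that the direction is not fixed.

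**The case against.** The strongest reply is that no written analysis is affected. The plan describes PCA across subjects followed by association, with no fold change, subtraction or activation score. PCA within one condition, and associations built on it, do not involve the 24 h versus 4 h comparison. This stands, and it limits the point to contrasts, change scores, induced-gene lists and PCA pooled across conditions. The stated purpose and the with/without pairing imply such a measure, but the plan does not say how activatability is scored.

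Second, this may be a gap in wording. The general sentence allows both 4 h and 24 h, and the RNAseq sentence gives no time, so an unlisted 4 h unstimulated well is not excluded. That also stands, and it is why confirmation comes first in the fix. But the specific sentence assigns 24 h to cells without stimulus, and a laboratory following it would produce the mismatch.

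Third, the two times may simply have been swapped in drafting. This does not help: the anti-CD3/CD28 contrast stays aliased with culture time.

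Fourth, an extra well competes for cells with the dexamethasone wells. That stands as a constraint on the fix.

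**Conclusion.** As written, the stimulated-versus-unstimulated measure of T-cell activation is fully aliased with 20 h of culture. The LPS measure is too if it uses the same 24 h baseline. The reach is 2, 1 or 0 of the two activation contrasts, depending on which unstimulated wells exist and which is used as baseline. The conclusion assumes that such a measure will be calculated, which the plan implies but does not state.

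Three stronger readings are tempting, and the documents do not support them.

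- **That the planned gene-expression associations are invalid.** Analyses within one condition are untouched, as are the fMRI, eNO, spirometry and questionnaire analyses and the power statement.
- **That correlations with neural activity will be attenuated.** This follows if activation and the culture-time effect are taken as independent, but both are measured from the same 4 h unstimulated level. With that shared term the correlation can fall, stay the same or rise.
- **That a 4 h control is known to be absent.** None is named, but the text does not rule one out.

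The dexamethasone comparison is not exposed to this gap if treated and untreated wells with the same stimulus are cultured for the same time; the plan should say so. Importance is minor: one exploratory laboratory measure in a pilot.

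**What to change.** 1. Confirm and state the intended culture time of every condition, including the unactivated cells sent for RNAseq, the LPS control and the dexamethasone wells.
2. Harvest an unstimulated well of the same duration as each stimulated condition (4 h as written), and use it as the unactivated RNAseq sample.
3. Calculate activatability only against that well, for example as a per-gene log ratio, and state whether PCA is run within condition or pooled.
4. Keep a 24 h unstimulated well in addition only if comparability with protocol 2014-0116 needs it, and not as the baseline for 4 h stimulation.

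**Cost in libraries.** The Sample Size section states: "Our target sample size is total 30 individuals with severe asthma". If the unstimulated well is moved to 4 h, the count stays at 3 per subject, 3 × 30 = 90. If both unstimulated wells are kept, it is 4 × 30 = 120, or 30 more. At the 22 completers assumed in the same section, it is 4 × 22 = 88 against 3 × 22 = 66, or 22 more. If 24 h stimulation turns out to be intended, unstimulated wells at both 4 h and 24 h are needed, with the same addition.

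**Cost in comparability.** The Sample Size section says the 2014-0116 samples were collected in the same manner but gives no culture times. Moving the well could lose comparability if that study used a 24 h unstimulated culture.

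**Cost in cells.** Item b says "10 to 20 million PBMC will be" recovered. If dexamethasone is tested with each stimulus separately, 3 × 2 = 6 wells join the 3 RNAseq conditions, making 9 before any addition. The documents give no minimum cell number per well or RNA amount, so the laboratory must confirm that the yield allows a further well.
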